## WILLOW Full RCT Patient Protocol

The information you provide during this study will be used for research purposes only; it will not be shared with your therapist or treatment team. Your treatment and your participation in our study are separate but parallel activities. You are doing them at the same time but there will not necessarily be any cross over between the two EXCEPT for during the research appointments I just described to you where we'll ask about how sessions are going and what type of activities you do in session, etc. Everything you do for the research will be either on the phone or on SurveyMonkey, where the surveys are located. Everything else <>for WILLOW patient participants specify measures, videos, worksheets, etc in WILLOW>> would be for your therapy separate from the research. If you ever need clarification, please ask your provider or contact us.

As you know, the length of research-based treatment is 12 weeks. After the 12-week period, you and your therapist or clinic will decide what your next steps for treatment will be. If you have questions about this, we encourage you to talk with your therapist or clinic before enrolling in the study. While the research trial is 12 weeks, this does not mean you must quit treatment after 12 weeks or that you are obligated to continue treatment for 12 weeks. If more treatment is needed after the 12-week period, you will work with your therapist and the clinic to decide how to proceed. If you decide to stop treatment before the 12 weeks of your study participation are over, we ask that you still complete the online surveys and phone calls, regardless of whether or not you are still receiving treatment from your study therapist.

As compensation for your study participation and time involved in completing the online surveys and phone calls, you will receive \$40 for each of your Week 4 and Week 8 surveys, and \$60 for your Week 12 survey, for a total of \$140 if you complete all study procedures. The payment will be coming from Chase Bank so be sure to keep an eye out for envelopes from Chase when the time comes.

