**Make sure to text or read aloud the study ID to the patient.**

If you have any questions or if you experience any difficulty with the survey system, please call or email us immediately. We're here to help! Once you have completed the surveys, please call or text or email me back at my direct line you'll find in the email I will send you to record the completion of that survey. I will also ask for the date of your next therapy session. After this, we will let your therapist and/or clinic know you are ready to schedule your first study session. After your first visit with your therapist, we will call you to schedule your next three study assessments and also send you the link to one final survey to complete as part of your first bundle of survey measures.

Do you have any final questions for me? Excellent! I will now email you the link to the consent form and your first set of surveys. Thank you for talking with me today. If you have any questions or concerns as you are reviewing the consent form or completing the surveys, please don't hesitate to contact me and remember to give me a call when you're finished with the surveys. Thank you!

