### 5. If participant does not respond soon, call and email their provider

#### **When participant calls you back after completing consent and baseline:**

1. Thank participant for completing the Consent process and baseline surveys; let participant know you will be sending them a copy of their Consent Form and HIPAA authorization via email shortly.
2. Proceed through debrief protocol if needed
3. Collect date of next therapy session and schedule assessments if they know.

~~~~~

Step 4: Action Steps after Informed Consent Call

1. Send the patient a link to the consent form/HIPAA authorization/baseline surveys in an email.
 - a. Study IDs = first three digits of therapist Study ID and fourth digit the number of patient assigned to the therapist.
Example: This patient is the third study patient the therapist is treating. The therapist ID is 117. → Patient ID = 1173
 - b. If patient hasn't yet been assigned to a therapist, they will be numbered in consecutive order, starting with 3001
2. Log that the phone call has been completed in the cover sheet and that the consent form and baseline are pending
3. Log that the phone call has been completed and the consent and baseline have been sent in the [Participant Tracking DB](#)

WILLOW Full RCT Patient Protocol

4. Check back in two hours if you haven't heard back from patient to see if they filled out the consent form and baseline assessment on survey monkey.
 - a. If they have not completed the consent form or baseline, call and email the participant to check in; reschedule as needed.
5. When they complete the consent form, check to make sure all answers are filled in the consent form and that they agree to participate in the study. Make note if they answer No to any of the authorization questions and discuss at next Research Meeting
6. Log the consent completion into the database and cover sheet
7. Log the Baseline completion into the database and cover sheet

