8. **If we have permission to discuss study participation with Therapist/Clinic**, let the Therapist and/or clinic know the patient is enrolled in the study and ready to start their study therapy sessions and request they let us know when the client's first session will be (call and email; do not include patient name in email). **If we do not have permission to discuss study participation with Therapist/Clinic**, ask patient to let their therapist/clinic know they are ready to start their study therapy sessions and request they let us know when their first session will be.
9. **Send patient copy of their consent form and HIPAA auth**
 - a. In SurveyMonkey copy everything under "Collect" until the end of the consent form section and paste it to the end of the Consent Form template
 - b. In SurveyMonkey copy what's under "Collect" (through time spent) and the HIPAA section and paste to the end of the HIPAA authorization template
 - c. Save both as PDFs with following naming conventions:
Lastname,FirstInitial.FullRCT.PatientConsentForm
Lastname,FirstInitial.FullRCT.PatientHIPAA

(Use full first name if last name is same as someone else's)

Step 5: Collect dates from Therapist

NOTE: check Clinic details in [Participant Tracking DB](#). Some clinics will have already completed this session prior to informing client of study. In which case the below is irrelevant because it should already have been done before this point.

1. Record the client's care start date in the Tracking DB under the patient and therapist tabs
2. Record when the client's first session with their research therapist will be (the "Welcome/Get to Know You" Session).
3. Contact therapist after the Welcome/Get to Know You Session
 - a. Did the client attend this session?
 - b. Is the client eligible / appropriate for the study?
 - c. When is the first Study Therapy Session?
4. Record information in [Participant Tracking DB](#)
5. If eligible, continue to Step 6

WILLOW Full RCT Patient Protocol

6. If ineligible, discontinue client's participation
 - a. Log that the patient is ineligible in the tracking database and move cover sheet to the "Ineligible" folder.

Step 6: Scheduling Call

1. Make scheduling call as soon as you can, script below
2. If the patient doesn't answer the call, send scheduling email and leave the voicemail below.
3. Call back/email every 2 days until you reach patient.

Voicemail Script:

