## Step 11: Post-Intake Steps

10. If the therapist doesn't get back to you within 24 hours of the intake session, send email to check if the patient was eligible or not.
11. Log the following info:
  - a. If patient showed up or not
  - b. Date rescheduled if patient didn't show up
  - c. Eligibility status
  - d. If patient is eligible, schedule ALL therapist assessments and record in Summative Tracking DB

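### Where the Welcome session follows consent, the Week 4, 8 and 12 surveys are booked after the first visit and the therapist's eligibility answer, with no route for an enrolled patient who does not attend

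*Protocol*

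**What the plan says.** **Order of events.** In the Patient Protocol the patient hears about the study and completes consent and baseline (Step 3). The clinic is then told that the patient is enrolled, where permission allows (Step 4). Under Step 5 staff "Contact therapist after the Welcome/Get to Know You Session" and ask "Did the client attend this session", followed by whether the patient is eligible. Two branches are given: "If eligible, continue to Step 6" and "If ineligible, discontinue client's participation". Step 6 is the call at which the three assessments are booked. The Step 3 script tells patients to expect the same order: "After your first visit with your therapist, we will call you to schedule your next three study assessments".

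**Therapist side.** Therapist Protocol Step 11 logs whether the patient showed up, a new date if not, and eligibility status, then says "If patient is eligible, schedule ALL therapist assessments and record in Summative Tracking DB".

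**Two exceptions.** The instructions for the callback after consent and baseline say "Collect date of next therapy session and schedule assessments if they know", which I read as knowing the session date. The note that opens Step 5 exempts clinics that held the Welcome session before telling the patient about the study.

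**Follow-up after stopping.** For patients who decide to stop treatment before the 12 weeks are over, the Step 3 script says "we ask that you still complete the online surveys and phone calls, regardless of whether or not you are still receiving treatment". The therapist orientation script (Therapist Protocol Step 7) likewise keeps patients who leave therapy early in the study.

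**Analysis.** The SAP (Analysis Strategy) analyses only patients who attended five or more sessions.

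**The concern.** Follow-up in a randomised comparison should not depend on something that happens after allocation and may be affected by it. Here therapists are randomised first, and a patient whose therapist is known is told the arm on the consent call (Patient Protocol Step 3). Turning up to the Welcome session comes later. A patient reluctant about computer-assisted therapy, or disappointed with usual care, can react to the arm by not attending.

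If booking then waits on attendance, such patients are enrolled and have a baseline but are never surveyed. At stake are the least engaged patients, and the possibility that their numbers or their prognosis differ between arms.

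**Working it through.** No sample size, attendance rate or dropout figure in the documents bears on this, so there is no stated figure to reproduce. The check is a trace of every route from consent to a booked survey.

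**1. What depends on booking.** The Step 6 script sets Week 4 at four weeks from the scheduling call. Step 9 makes each assessment call at its scheduled time, and the chasing of missed assessments starts from there. With no booking there is no date, and nothing triggers a survey.

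**2. Routes to booking.**

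- *Route A: Welcome session after consent, not booked at the callback.* Attends and eligible: goes to Step 6. Attends and ineligible: participation ends. Does not attend: Step 5 gives no instruction. Therapist Protocol Step 11 logs a rescheduled date, with no rule for a patient who never comes.
- *Route B: assessments booked at the baseline callback.* Dates may exist before the Welcome session, so a never-attender could still be surveyed.
- *Route C: Welcome session held before the study was introduced.* The gate is already passed, so the patient can be booked without attending a later study session.

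The documents do not say how many patients take each route, or which is usual. The Therapist Protocol itself varies: Step 7 has the therapist introduce the study at the Welcome session, Step 9 puts a welcome discussion before referral, and the First Session text in Step 9 puts the intake session after screening.

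**3. Comparison with patients who stop.** On Route A a patient who attends once, is found eligible and then leaves is booked and followed to Week 12. A patient who leaves one visit sooner is not booked.

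**4. Size.** Let p be the share never attending in each arm, and d the mean outcome of never-attenders minus that of attenders, assumed equal in both arms. Each arm's all-enrolled mean is its attender mean plus p × d. The attender-only and all-enrolled differences between arms therefore differ in absolute value by

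|p(WILLOW) − p(usual care)| × |d|.

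Neither factor is in the documents. Purely as an illustration, assume a rate gap of 5 to 20 percentage points and d of 2 to 5 PHQ-9 points:

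- low end: 0.05 × 2 = 0.1 points;
- high end: 0.20 × 5 = 1.0 point.

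The high end is strained. With equal arms and 10% never attending overall, a 20-point gap needs 0% against 20%, since (0 + 20) / 2 = 10. The PHQ-9 is also only an assumed scale: the documents name it as the screen (Step 2) and, as the PHQ-9S, among the measures in WILLOW, but not as the Week 12 outcome.

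**5. Effect on the planned estimate.** A never-attender has zero sessions and fails the SAP's five-session rule whether or not surveyed. Collecting these outcomes without changing that rule moves the planned estimate by nothing.

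**The case against.** The strongest reply is that the gate has a purpose. The therapist makes a last eligibility check at this session (Therapist Protocol Steps 7 and 9), and a patient who has not attended has not had it. That stands, and is a real cost of the fix. These patients have, however, passed the study's own screen, consented and been counted as enrolled.

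Second, no passage says to drop no-shows. The weekly review of pending cover sheets (Patient Protocol Step 7) asks staff to work out what each participant needs. So the loss is inferred from a missing branch and is not a stated rule. This also stands, and it limits the conclusion to likely loss.

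Third, early booking may be common, since the consent scripts ask for the next session date. The documents cannot settle that.

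A reader might infer that the protocol contradicts its own promise to survey patients regardless of treatment. It does not: that sentence, and its counterpart for therapists, apply to patients who stop or exit therapy. Their silence on those who never start is a gap. A reader might also take the callback as the only exception, but the note in Step 5 is a second.

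**Conclusion.** The gap is real and should be closed. On Route A an enrolled patient who never attends is likely to have a baseline and no outcome. For patients with a known therapist this happens after the arm is disclosed, so the loss can be differential. Patients not yet assigned to a therapist (IDs from 3001) hear about both arms, so the disclosure argument does not apply to them at that point.

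The size cannot be derived from the documents. A reader might take the 0.1 to 1.0 point illustration as an estimate of bias in this trial. It is not one: every input is assumed, and so is the scale.

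Nor do the documents support saying that no analysis could address the loss. The baseline is held, so sensitivity analyses for missing outcomes remain possible, though they are weaker than having the outcome. Finally, better follow-up alone would not repair the comparison. It makes an as-enrolled analysis possible, and the SAP has to use it.

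**What to change.** **Patient Protocol**

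- Make booking at the baseline callback the default for every consented patient. Anchor Weeks 4, 8 and 12 to the planned first study session, or to the baseline date if no session or therapist is yet assigned. Re-anchor if the session is rescheduled.
- Add a did-not-attend branch to Step 5 that continues to Step 6. Leave the route for patients found ineligible as it is.
- Reconcile the Step 3 script and Step 5, which book after the first visit, with the callback instruction, which allows booking before it. Align the Step 6 wording that counts from the day of the call.

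**Therapist Protocol.** In Step 11, limit the therapist record for a never-attender to non-attendance, and state whether that record is paid.

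**SAP.** Replace the five-session restriction with an as-enrolled analysis, or at least add one as a sensitivity analysis. Report by arm how many enrolled patients never attended and how many of those have outcomes. The SAP is written in the past tense, so where data are already collected this reporting and a missing-data sensitivity analysis are what remain open.

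**Cost.** Up to $40 + $40 + $60 = $140 per never-attender, plus three assessment calls and reminders. If 10 to 20 of every 100 consented patients never attend (an assumption), that is at most 10 × 140 = $1,400 to 20 × 140 = $2,800 per 100. Some of those followed will not have had the therapist's final eligibility check, and should be identifiable in the data.

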### **Ask them the date for the next session and record in coversheet**

- If you're able to complete your first set of surveys today [before next session], then I'll go ahead and send you that link to the quick survey for you to do.
- Now, the next three times we'll ask for you to complete surveys will be at Weeks 4, 8, and 12 during your participation. These will take between 45-60 minutes to complete and will involve a 10-15 minute phone call with a member of our research team and then an online survey that will take about 30 minutes answering questions about your mood, your satisfaction with the treatment you are receiving, and questions about your experience with your therapy and therapist.

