Hi _____, this is _____ from the Evidence-Based Practice Institute. Thanks again for your participation! I am calling today for your <4, 8, or 12> week study surveys. Is now still a good time to talk?

Great! Today involves two steps. First, we'll talk for a few minutes here on the phone. I just have a few questions for you and welcome any other feedback about your experience in the study so far. Then, I will send you an email with a link to complete your surveys online. Once you have completed the surveys, I'll ask that you call me back so that we can talk for a few more minutes before we end for the day. Do you have any questions before we get started?

Wonderful! First, I want to thank you for the time you have invested into our study and your important contributions. We'd like to ask you several questions about your experience.

<<Administer Semi-Structured Interview, taking detailed notes during conversation >>

Thank you for answering those questions! Is there anything else I should note about your experience in the study? Thank you.

Now I will now send you an email with the link to your surveys for today. Please let me know when you get it.

Great! We anticipate these surveys will take 30-45 minutes to complete. The survey will ask you to enter your Study ID and you'll find this in the email. Please call me back as soon as you complete the surveys to record your completion. I included my phone number in the email that you can use to call my directly. Thanks! Talk soon!

- After the call, send patient the email with link to assessment surveys.

Log that you sent the email in cover sheet/[Participant Tracking DB](#)

WILLOW Full RCT Patient Protocol

Action steps while participant completes surveys:

1. Check the debrief items at the end of the survey
2. If participant reports a score of 5 or greater on items 3a, 3b, or 4b call them and do [mood induction protocol](#) (see [flowchart](#) for the coping skills)
3. If they do not answer leave a voicemail (script below)

VoiceMail Text (if patient does not answer when research team calls):

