## WILLOW Full RCT Therapist Protocol

<<If needed, remind WILLOW therapists that they can they can use WILLOW with non-research clients (i.e., create WILLOW account) and that the patients can login to WILLOW at any time to complete their measures>>

Thank you for answering those questions! Is there anything else I should note about your experience in the study? Thank you.

Thank you so much for answering those questions! Now, I will send you the link to the Week \_\_\_ surveys for you to complete when you have a moment after our call today. You will need to enter your study ID and the study ID of your client. They are xxxx and xxxxx, I have included these in the email. If you run into any problems, please give me a call directly.

Our next study call is scheduled for Day, Date, Time. We'll send you a reminder the week before your next call. Thank you!

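### At follow-up, patients and therapists rate outcomes only after an interview with staff not described as masked, so ratings may shift differently by arm

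*Protocol*

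**What the plan says.** **Patients.** The call script in Patient Protocol, Step 9 fixes the order at each follow-up. It begins "First, we'll talk for a few minutes here on the phone", instructs the caller to "Administer Semi-Structured Interview, taking detailed notes during conversation", and tells the patient "Then, I will send you an email with a link to complete your surveys online". A second contact is also scripted: "Once you have completed the surveys, I'll ask that you call me back so that we can talk for a few more minutes". Step 3 describes the survey as covering "questions about your mood, your satisfaction with the treatment you are receiving, and questions about your experience with your therapy and therapist". It says that at the research appointments "we'll ask about how sessions are going and what type of activities you do in session".

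**Therapists.** Therapist Protocol, Steps 13 and 14 put a semi-structured interview before the survey is done. Both scripts add that, if needed, staff should "remind WILLOW therapists that they can they can use WILLOW with non-research clients" and that patients may log in at any time. Usual-care therapists have no counterpart.

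**Analysis.** The SAP (Analysis Strategy) takes the Time X Condition effect as primary for outcomes with a baseline. It takes the Condition effect for outcomes measured only at follow-up, such as alliance and use of evidence-based therapy tasks.

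**The concern.** Talking about one's treatment shortly before rating it can colour the rating. The callers belong to the group that built WILLOW: the Patient Protocol (Step 1) and the Therapist Protocol (Step 2) both say so to participants. A WILLOW participant is therefore discussing the caller's own product, and a usual-care participant is not. That makes a courtesy effect that differs by arm plausible.

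Such an effect would enter the estimates that the SAP calls its effects of primary interest. More follow-up points would not remove it, because the same step recurs at each one. Participants in a trial of this kind cannot be blinded, but the order of interview and survey is a choice.

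**Working it through.** The documents state no figure on this point, so there is none to reproduce. The check sets the procedures side by side and then traces how a shift would reach the estimates.

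**1. What comes before each rating**

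| Rating | Contact scripted before it |
|---|---|
| Patient baseline | Consent call (Step 3). The arm is disclosed and described if a therapist is already assigned. No therapy interview. |
| Patient satisfaction survey after first study session | Link sent by email (Step 8). No interview specified. |
| Patient Weeks 4, 8, 12 | Semi-structured interview (Step 9) |
| Therapist baseline | Warm call (Step 6). The arm is stated, and WILLOW training is described to new WILLOW therapists. |
| Therapist Weeks 4, 8 | Interview, then the WILLOW-only reminder if needed (Step 13). The survey is done when convenient after the call. |
| Therapist Week 12 | Interview, then the same optional reminder (Step 14) |

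What is new at follow-up is the interview and the reminder. Contact with staff, usually with the arm known, is present at baseline too.

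**2. Whether the patient's caller knows the arm**

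- Staff are told to state the condition at consent (Step 3).
- Patient IDs normally begin with the therapist's ID (Step 4), and the interview file is saved under the study ID (Step 9).
- Staff send the first-session survey after a session that Step 8 describes by arm.
- No masking of assessors is described.

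This is a strong inference, not a stated fact. Patients without a therapist get IDs from 3001 onward, which carry no therapist number.

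**3. How a shift reaches the estimates**

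Let δ be the mean rating shift in WILLOW minus that in usual care, caused by the contact before the rating.

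- Outcomes with a baseline: bias in change at time t = δ(t) − δ(0).
- Follow-up-only outcomes: bias in the averaged Condition effect = [δ(4) + δ(8) + δ(12)] / 3.

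With assumed values in SD units:

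- δ(t) = 0.20 and δ(0) = 0 gives 0.20.
- δ(t) = 0.20 and δ(0) = 0.10 gives 0.10.
- δ(t) = 0.10 and δ(0) = 0.20 gives −0.10.
- Follow-up only, δ = 0.20 throughout: (0.20 + 0.20 + 0.20) / 3 = 0.20, so averaging does not dilute it.
- Equal shifts in both arms, δ = 0 throughout: no bias.

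**4. Illustration of the consequence**

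Assume no true effect, a two-sided 5% test of two means, independent observations and a net differential b in SD units. With standard error √(2/n), the false-positive rate is P(Z > 1.96 − b/√(2/n)) + P(Z < −1.96 − b/√(2/n)). For n = 50 and b = 0.2, √(2/50) = 0.20 and b/0.20 = 1.0, so the rate is P(Z > 0.96) + P(Z < −2.96) = 0.170.

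| n per arm (assumed) | b = 0 | b = 0.1 | b = 0.2 | b = 0.3 |
|---|---|---|---|---|
| 30 | 5.0% | 6.7% | 12.1% | 21.3% |
| 50 | 5.0% | 7.9% | 17.0% | 32.3% |
| 100 | 5.0% | 10.9% | 29.3% | 56.4% |

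The documents give neither b nor n. The table shows sensitivity and does not estimate the bias in this trial.

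**The case against.** The strongest reply is that differential bias is possible but not shown. Its main parts are these.

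- **The interview content is unseen.** The template is linked but not reproduced. Step 9 introduces the interview as being about experience in the study. The Step 3 sentence about sessions and in-session activities describes the appointments as a whole, so it may refer to survey items. This stands: overlap between interview and survey is likely but unproven.
- **The interview step is the same in both arms.** This stands. Bias requires a response that differs by arm.
- **Baseline is not free of arm-specific contact.** A reader might infer that follow-up ratings are primed while baseline ratings are clean, so that any follow-up shift passes in full into the change score. The documents do not support that. Baseline follows its own staff call, usually with the arm disclosed, and even the sign of the net bias is unknown. For outcomes without a baseline, such as alliance, the comparison does not arise.
- **The reminder is mild.** A reader might take it as instruction to extend the intervention. It is conditional and permissive, it repeats information given earlier, and its first part concerns clients outside the trial. It can bear directly only on therapist reports, and at Weeks 4 and 8 the therapist survey need not follow at once.
- **Not every outcome can be classified.** A reader might conclude that no masked measure exists. The documents do not list all outcomes or say who rates alliance, so this cannot be confirmed.
- **Re-ordering leaves the open-label self-report problem in place.** This is true, but it is no reason to keep an avoidable addition to it.

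The order of events and the lack of any described masking remain. The consent call asks nothing about experience of therapy, so it cannot be assumed to cancel an effect of the interview.

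**Conclusion.** The concern holds in a limited form. Follow-up self-ratings come after an interview by staff who are not described as masked and who very likely know the arm, and therapists in one arm may also get a reminder before their survey. Neither step precedes baseline. This is a real and avoidable route to bias in the Time X Condition and Condition effects.

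Its size and direction are unknown. It equals the arm-differential shift at follow-up, less any such shift at baseline, and is zero if the interview acts alike in both arms. The conclusion rests on two inferences: that the caller knows the arm, and that the interview touches what the survey measures.

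**What to change.** At Weeks 4, 8 and 12, open with a short neutral greeting, send the survey link, and hold the semi-structured interview on the call-back that Step 9 already asks for. For therapists, have the survey submitted before the interview, and move the WILLOW-only reminder to after submission or into a routine support email.

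The costs are small, but there are two:

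- Some interviews will be lost when a participant completes the survey and does not call back.
- The Mood Assessment sits at the end of the online survey, and the Mood Assessment and Debrief Protocol requires it before each assessment concludes. Simply moving the interview to the call-back would place it after that check. The two procedures must be reconciled so that the Mood Assessment and any debrief still come before the assessment concludes. How to do that is for the study's clinical leads.

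The SAP is written in the past tense, so the data may already be collected. In that case, report the order of interview and survey, and the absence of any described masking, as a limitation of the self-rated outcomes.
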